# 10.4 Data Management and Reporting

10.4.1 Web-based data management system

The DCC has started and will continue to develop a web-based data management system (nicknamed Nephron). This system is built on extensible markup language (XML) technology, whereby every aspect of data forms (e.g., question text, possible responses, validation code) are stored in XML files [Gange 2000]. Like HTML, XML is tag-based, license-free, and platform- and vendor- independent. The XML files will function as a central repository from which all components of the data management system will be defined. Two main advantages of this approach are that (1) all components of the data system are guaranteed to be compatible, and (2) changes to the XML files are automatically translated throughout all components of the data management system.

The components developed from the central XML files include the database, data forms (online and hard-copies), codebooks, editing/queries, and reporting methods. We use the flexible, scalable and reliable MS SQL Server as our database storage system. Data fields are defined by the types, sizes and formats specified in the XML files. Our data entry forms are created in HTML. Hard-copy data forms and online data entry screens are identical (although hard-copy forms will divide the form with user-specified page breaks), thus enhancing the quality of the data entry. At the time of data entry, online data editing is accomplished using JavaScript code embedded in the HTML form

according to rules stored in the central XML files. These edit checks include field-level validations and within-form checks of logical consistency. Data transmission is done using MS data binding, which associates each data entry field on an HTML form with a corresponding field in a database table. The process of connecting the HTML forms with the database is done using remote data services, which is a subset of ActiveX data objects. After data is entered, additional central editing will be done to evaluate cross-form and longitudinal consistencies. Edit queries that are generated from these edits will be stored in tables accessible by remote data entry staff for resolution. A system for the generation of online reports will be developed to enable the clinical coordinating centers to explore the database.

The DCC is the central resource for compiling suggested changes to questionnaires and for developing and incorporating new questions for distribution to the clinical coordinating centers. As the protocol evolves and expands, the DCC staff develops data collection instruments. This ensures continuity of style and formatting across forms. Since instruments are centrally written and developed, changes and additions are juxtaposed with existing data collection methods and new questions are standardized with previously written questions. This enhances the flow of survey instruments and helps reduce respondent bias. Prior to the initiation of a new visit cycle (see diagram in section 5.4.1), data managers will create codebooks and input files to document variable names, questions and response codes. In previous multicenter studies coordinated by the DCC or CKiD, these codebooks have served as the resource for compilation and interpretation of the data collected. Investigators are encouraged to use the codebooks and refer to the data by the variable names to prevent miscommunication.

### 10.4.1.1 Security and Back-up

Nephron is protected using multiple layers of security. At the highest level, we utilize the Johns Hopkins University firewall that oversees access to all School of Public Health computers, have disabled ftp and telnet access to our dedicated study group server to prevent unauthorized access, and can implement IP-restrictions that control which computers can access Nephron. The web server on which Nephron is located has a secure 128-bit certificate, permitting us to use Secure Sockets Layer (SSL) encryption. This security ensures that all data (including usernames, passwords, and study data) are transmitted between browsers and web servers with maximum safety and prevents unauthorized personnel from gaining access to the data. We take advantage of Windows 2000 file system security whereby every user of Nephron, including staff at the clinical coordinating centers, has a managed user account on our servers with specific permissions and file access. Lastly, all fields changed by subsequent entry are recorded for tracking and to facilitate data recovery.

The Nephron database is automatically backed-up via a full copy to the Unix server disk on a daily basis. The entire system (including all users, Nephron SQL Server, and data files) is backed up daily using an 8mm AIT tape jukebox. The duplicated Nephron database will continue to be included in back-up script programs that automatically execute after each midnight. In addition to the daily automatic system backup of file systems, project specific data is also backed up to separate 8mm Exabyte tapes. On a monthly basis, exact copies of the daily system backup tape and the project specific tapes are produced and stored off site in case of a local catastrophe. Backup and recovery are periodically tested.

#### 10.4.1.2 Public data tape

To make the CKiD study data available to a wide range of external investigators and to respond to public requests for data, the DCC will assemble datasets for public use that will be archived and distributed by the NIDDK Data Repository, the Information Management Services (IMS). In July 2013, NIDDK established a public data sharing policy. The policy documents a suggested schedule regarding when study data should be provided to the data repository. KIDMAC has experience with creating public datasets and will de-identify the datasets to ensure that no linkages can be made with participants and that they are compliant with HIPAA regulations. The lack of identifiers between coded IDs included in the public data and coded IDs that exist in the study dataset ensures a high level of protection. The following are additional procedures used to ensure that no identification can be made: (1) recoding IDs with a randomly generated CASEIDs which are securely stored at the data center and not distributed or stored on the same medium as other study data; (2) eliminating any linkage to the clinical site and clinical coordinating center where a participant is followed; (3) removing the dav and month values from baseline and birthdates; (4) converting all other dates into time durations from the participant's baseline date; and (5) eliminating all medical record, registry, and disenrollment data except year of death.

#### 10.4.2 Quality Assurance

The DCC has experience with quality assurance and control initiatives undertaken throughout all aspects of cohort studies, including data management, clinic oversight, staff training and collaboration with central laboratories and national repositories. These experiences with quality assurance methods are summarized in five key areas.

First, the DCC will ensure quality at time of data collection. The DCC will spearhead the development of the manual of procedures, which is the heart of ensuring standardization across multiple sites. The DCC will coordinate the development of new data collection forms. Based on the DCC's experience with prior multicenter studies, we anticipate our overall residual error rate to be consonant with rates published from other multicenter cohort studies, on the order of 10 per 10,000 [Gibson 1994,Horbar 1995, Reynolds-Haertle 1992]. Second, the DCC will ensure quality at time of data entry. Our data management system has been designed with features to ensure quality data entry. including automatic field advance based on programmed skip patterns, range checks, and immediate edit reports for local resolution. Third, the DCC will ensure quality at time of data freeze. We will apply edit programs annually, updating the program in parallel with annual form and protocol changes. Fourth, the DCC will ensure quality at time of data summarization. Summary files are scientifically motivated files that summarize key study variables for the purpose of enhancing the management and standardization of data across various research initiatives. (see section 4.3.3 for more details.) Fifth and last, the DCC will ensure quality at time of data analysis. The DCC promotes the use of appropriate study designs and analytical methods to ensure quality interpretation and inference, which has included providing close collaborations and scientific partnership in analyses. CKiD Protocol 101 06/01/16 to 08/01/17 **OSMB** Approved
## 10.4.3 Summary Analytical Files

Data will be periodically frozen for construction of analytical data files, and the DCC distributes datasets to the clinical coordinating centers for use with local analyses that may occur concomitantly with central analyses ongoing at the DCC. To standardize the analysis of such complex data and reduce the likelihood of software coding errors, we will develop common summary data files, derived from the web-based database, for analyses. The final structure of these files would be determined in collaboration with the study investigators. These files will be distributed to investigators at the clinical coordinating centers so that specification of common variables for different scientific initiatives will be uniform. We foresee the need for the following files, although additional summary files may be created as the need arises.

First, VERT DATEBASE is a vertical data file which will contain one record per person with the dates of each visit and the date of last contact. This file will contain the core data to assess follow-up rates and to determine who was seen at each visit defined by a specific calendar period. Second, KIDHIST will contain a record for each participant with key variables for describing the natural history of pediatric kidney disease. Interval encapsulating key events will be defined by dates last free of the event and when the event was first diagnosed. Such outcomes include: date of CKD diagnosis, initiation of treatment for CKD, first GFR < 15, first use of dialysis, transplantation and death. If the person has never had the event, then the date last free of the year of the event would be the date of last contact and the date first seen with the year of the event will be set to 2100, indicating a right-censored observation. If the date last free of event equals the date when the participant was seen with the event, then this is an uncensored observation. If the dates are different and the second date is less than 2100, this corresponds to an interval-censored observation. This file will be critical for implementation of survival analysis methods. Third, additional summary files (i.e., GFRSUMMARY, NEURO, CARDIO, ECHO, GROWTH, MEDSUM) will contain variables summarizing results from markers related to the scientific domains of CKiD (i.e., kidney, neurocognitive, cardiovascular, growth and medications) obtained at each visit. Thus these files will be vertical files with each record corresponding to one personvisit. These files will be critical for longitudinal analyses of these outcomes.

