#### 5.4.3 Continued Follow-up Protocol

Participants will be given the option to participate in the continued follow-up protocol after they have renal replacement therapy, pregnancy, unable to reach or withdrawal (i.e., lost to regular follow-up). However, children who have a cancer diagnosis will be ineligible to participate in the follow-up protocol. The follow-up protocol will be composed of two components: an interview/survey and chart review. For convenience, the follow-up interview/survey will be completed via phone, in-person interview, mail or on-line. During the interview/survey, renal therapy status data will be obtained. Additional data such as sociodemographic information, medical history, health care utilization status, medication use, physical symptoms and quality of life data may also be collected. In conjunction with the follow-up interview/survey, the coordinator will collect data (i.e., lab results) from chart review to ascertain accurate data and the data may be reviewed by a researcher selected by the CKiD study who is not affiliated with the clinical site. Ideally, the follow-up protocol should be scheduled to occur annually based on the anniversary date of the participant's baseline (V1a) visit (± two months). However, for participants who disenrolled prior to the addition of the follow-up protocol, their first follow-up will be completed as soon as possible and the subsequent follow-up interviews/surveys will occur annually based on the anniversary baseline (V1a) date (± two months).

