# 5.4.4 Post Renal Replacement Therapy (RRT) Protocol for Dialysis and Transplant Participants

At selected sites, participants will be invited to participate in the renal replacement therapy protocol after they begin regular dialysis treatment or have a kidney transplant (i.e., RRT event date). The post RRT visits will be similar but not identical for transplanted and dialyzed participants who initiate therapy after the RRT protocol is implemented.

For transplanted participants, the first baseline visit (TV1a) will consist of the collection of iohexol GFR, cystatin C, serum creatinine and proteinuria data. At the second baseline visit (TV1b), transplanted participants will complete the BRIEF and NIH tool box tests. At the subsequent even visits, extensive cardiovascular measurements (i.e. ABPM, ECHO, cIMT, cMRI and vascular tests), BRIEF and specific TV1a visit data will be collected. The subsequent odd visits for the transplanted participants will be a combination of their specific TV1a and TV1b visits (see Table 5.4.4a).

For dialyzed participants, the first baseline visit (DV1a) will consist of a 24 hour urine collection to calculate residual urine volume, Kt/V measurements and NIH Toolbox test data. However, if the NIH toolbox was completed within 6 months prior to the initiation of dialysis, it should not be completed at the D1a visit. The second baseline visit (DV1b) will include the collection of extensive cardiovascular measurements (i.e., ABPM, ECHO, cIMT, cMRI, vascular tests). The subsequent even visits will include NIH Toolbox and cardiovascular data collection but no cMRI and vascular test data. The subsequent odd visits for dialyzed participants will be parallel to the second baseline visit (DV1b) with the addition of some laboratory markers (see Table 5.4.4b).

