## 8.1.2 Analysis of Time-to-Event Data

In the proposed cohort study, several time-to-event outcomes of potential interest are (1) ESRD, (2) transplantation, (3) the initiation of dialysis, (4) GFR falling below 15 ml/min|1.73m^2, and (5) a pre-specified reduction (say 50%) in GFR. The survival analysis methods described in this section apply with equal force to each of these endpoints of interest and represent an important component of the armamentarium to address the study aims.

The use of time-to-event methods in cohort studies requires considerable attention to the underlying assumptions and censoring mechanisms. One particular issue concerns the incompleteness of outcome data. Careful consideration should be given to the censoring strategy, since censoring at the last time individuals were seen could lead to biased estimates if cases are actively sought and collected up to the date of the analysis [Muñoz 1997]. For instance, were event ascertainment complete, it would be more appropriate to censor follow-up time at the date of analysis [Hoover 1993], rather than at the date last seen. For most studies, an appropriate censoring strategy will be somewhere between these two extremes (i.e., the last contact and the date of analysis). The optimal approach will depend on the study design developed by clinical investigators in concert with KIDMAC investigators. For the analysis of time-to-ESRD, the trajectories of censored observations can be used to estimate when an individual will reach the threshold that defines an event. In doing so, we will circumvent informative censoring since we will use internal data to complete the missing information of when an individual reaches the threshold that defines an event. The complementary use of methods for longitudinal data and survival analysis will be a subject of methodological research by KIDMAC investigators.

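### KIDHIST censors the first GFR < 15 event at last contact, which can fall after native-kidney GFR has stopped being observed, so the standalone GFR < 15 rate would be understated if the file dates are used as written

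*Protocol*

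**What the plan says.** Protocol 10.4.3 describes KIDHIST as one record per child, with each key event bracketed by a date last free of it and a date first seen with it. The listed outcomes include "first GFR < 15, first use of dialysis, transplantation and death". For a child who never had the event, "then the date last free of the year of the event would be the date of last contact", and the second date is set to 2100 to mark right-censoring. No exception is made by type of event. The section adds: "This file will be critical for implementation of survival analysis methods". A companion file holds "the dates of each visit and the date of last contact", so last contact is kept apart from the visit dates, but it is not defined further.

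Section 8.1.2 lists, as a time-to-event outcome separate from ESRD, transplantation and dialysis, "4) GFR falling below 15" ml/min|1.73m².

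Contact can outlast regular visits. Under 5.4.3, children who have had RRT, become pregnant, withdraw or cannot be reached may join an optional protocol, ideally annual, in which "the follow-up interview/survey will be completed via phone, in-person interview, mail or on-line", together with chart review that collects laboratory results. Under 5.4.4, selected sites invite children to further visits after dialysis or transplant. For transplanted children, "the first baseline visit (TV1a) will consist of the collection of iohexol GFR" and other kidney markers. The dialysis visits list residual urine volume and Kt/V, and no GFR test.

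**The concern.** Dialysis, transplantation and death can be established from a contact: if the family answers and reports none of them, the child is free of them on that date. A marker threshold is different. A child is known to be free of GFR < 15 only up to the last date on which native-kidney GFR was measured or estimated, and after RRT the native kidney is no longer the organ being followed.

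Take a child transplanted with a last recorded GFR above 15. If post-transplant contact counts as last contact, the rule carries this child as free of GFR < 15 for every later year. Those years enter the denominator but can contribute no event. Time after leaving regular visits behaves the same way unless chart review supplies a creatinine. The standalone GFR < 15 rate is then diluted.

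**Working it through.** **Which figure to reproduce.** The protocol gives no rate, event count or person-time for standalone GFR < 15. What can be checked is the direction and an illustrative size.

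**Direction.** Let f be the share of counted person-time in which a native GFR < 15 could not be seen. The event count is unchanged, so

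apparent rate = true rate × (1 − f).

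For a true rate of 6 per 100 person-years, f = 5%, 10%, 20%, 30% and 40% gives 5.70, 5.40, 4.80, 4.20 and 3.60. The bias from this excess time is always downward.

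**Does 8.1.2 override the file rule?** It asks for care over censoring, but places the appropriate date for most studies between last contact and the date of analysis. Neither bound is earlier than last contact, and GFR < 15 needs an earlier date. The trajectory-based completion it describes is for time-to-ESRD. The competing-risks text, also in 8.1.2, concerns dialysis versus transplant.

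**Illustrative size, post-RRT time only.** Assumptions, none of them given by the protocol for this purpose:
- RRT times are exponential at r = 0.06 per year. The number is the middle column of Table 9.2, which is a planning incidence among the unexposed and not an RRT rate.
- The horizon is H = 10 years, with contact retained throughout.
- A share s of RRT children have no recorded GFR < 15 beforehand. The others are treated as leaving the risk set at about the time of RRT.

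Mean time to RRT or the horizon: m = (1 − e^(−rH))/r = (1 − e^(−0.6))/0.06 = 7.52 years.
Mean post-RRT time per child: 10 − 7.52 = 2.48 years.
Ratio of at-risk time to the file's denominator: m/[m + s(H − m)].

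| s | ratio | rate too low by |
|---|---|---|
| 30% | 7.52/(7.52 + 0.74) = 0.91 | 9% |
| 50% | 7.52/(7.52 + 1.24) = 0.86 | 14% |
| 70% | 7.52/(7.52 + 1.74) = 0.81 | 19% |

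Sensitivity:
- H = 13 years: m = (1 − e^(−0.78))/0.06 = 9.03. The shortfall is 12% at s = 30% (9.03/10.22) and 24% at s = 70% (9.03/11.81).
- Half of the RRT children keep contact, H = 10: s is in effect 15–35%, and the shortfall is about 5–10%.
- s = 50%, H = 10, with r = 0.03 or 0.09 (the outer columns of Table 9.2): m = 8.64 or 6.59, and the shortfall is 7% (8.64/9.32) or 21% (6.59/8.30).

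A simulation with competing exponential times (100,000 children per scenario, 10 years, contact kept to the end) agrees. With RRT without a recorded GFR < 15 at 3 per 100 person-years, a GFR < 15 rate of 3.00 appears as 2.58 and one of 5.97 as 5.10, which is 14–15% too low.

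**Leaving regular visits.** If 3% or 5% per year leave visits, contact continues and no chart-review creatinine is found, GFR is observed for (1 − e^(−0.3))/0.3 = 0.86 or (1 − e^(−0.5))/0.5 = 0.79 of the counted time over 10 years. In the simulation, adding loss at 3 per 100 person-years raises the shortfall from 14–15% to about 26%. RRT at 6 and loss at 5 per 100 person-years gives 40–42%. These are upper ends, because 5.4.3 provides for chart-review laboratory results.

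**The case against.** The strongest reply is that 10.4.3 describes a file and does not fix an analysis. It says so: "The final structure of these files would be determined in collaboration with the study investigators". KIDHIST holds the dialysis and transplant dates in the same record, so an analyst can truncate at RRT. Section 8.1.2 warns about censoring bias and leaves the optimal approach to later design, and 8.1.1 plans joint models because children leave through dialysis or transplant. This stands to the extent that the understatement is conditional on using the file dates as they are. It does not remove the point. The rule is explicit, it has no exception for a marker threshold, and 10.4.3 has these files distributed to investigators so that common variables are specified uniformly.

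A reader might infer more than the documents support:
- *That last contact certainly includes survey and post-RRT contact.* This is the natural reading, since the date is held apart from visit dates, but it is not stated. Continued follow-up is optional, and post-RRT visits run at selected sites, with those from V2 onward pending funding.
- *That survey follow-up yields no GFR information.* Section 5.4.3 pairs the survey with chart-review laboratory results, so some creatinine-based values should exist.
- *That the main ESRD analysis is biased by post-RRT time.* Sections 8.1 and 6.2.3.2.1 count dialysis and transplantation as events, so follow-up for that outcome ends at RRT.
- *That a 50% GFR decline is misdated by the same rule.* Section 8.1.2 names that outcome, but KIDHIST does not list it.
- *That a low graft GFR would be recorded as the event.* Nothing says graft values feed this field. If they did, they would add events and push the rate up, not down.
- *That exposure comparisons are biased.* This requires the unobserved time to differ between groups, and the protocol gives no figures on that.

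**Conclusion.** The point holds in conditional form. Applied as written, the KIDHIST rule gives first GFR < 15 a censoring date suited to dialysis, transplantation and death but not to a marker threshold. If last contact includes continued follow-up or post-RRT visits, the standalone GFR < 15 rate would be understated.

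The true size cannot be computed from the protocol. Under the assumptions of RRT at 6 per 100 person-years, 10 years of retained contact and 30–70% of RRT cases without a recorded prior GFR < 15, the shortfall is 9–19%. It is smaller where contact lapses and larger where children leave visits without any chart-review creatinine. The scope is one of several time-to-event outcomes in 8.1.2. The rule should be corrected before the file is used for that outcome.

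**What to change.** In 10.4.3, for first GFR < 15:
- Set the date last free to the date of the last native-kidney GFR, whether measured, estimated or derived from a dated chart-review creatinine, and never later than the RRT date.
- Treat RRT as a competing event for this outcome, or use the composite.
- State that post-transplant graft GFR does not fill this field.
- Keep last contact as the last-free date for dialysis, transplantation and death, and define which contacts it includes.

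In 8.1.2, add that censoring of marker-threshold events may precede last contact.

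The cost is one derivation change. KIDHIST already holds the dialysis and transplant dates, the GFR summary file holds results by visit, and chart-review laboratory results are collected under 5.4.3. Stated follow-up for this endpoint becomes shorter.
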